7.9.3. Stem Cell Transplant Rate

Stem cell transplant (SCT) rate is the percentage of patients proceeding to SCT within 90 days after their last dose of study drug regardless of whether the patient remains enrolled in this study. Unless documentation of SCT is provided, patients who are lost to follow-up within the 90 days following their last dose of study drug are counted among those not receiving SCT.

Hypothesis testing will be based on the stratified CMH general association test statistic (see Table 7). Stratification levels will be the same as those used for the randomization scheme (see section 6).

Within–treatment-arm statistics will include the number and percentage of patients counted as not receiving SCT due to being lost to follow-up; proportion of patients receiving SCT within 90 days after their last dose of study drug; and exact 95% CI estimated without stratification. Between–treatment-arm statistics will include the Mantel-Haenszel odds ratio and 95% CI estimated with stratification.

Table 7. Statistical Analyses of Stem Cell Transplant Rate

Analysis Population	Analytical Method	Role of Analysis
Intent-to-Treat	Stratified CMH	Primary
Per-Protocol	Stratified CMH	Supportive
Subgroups based on patient characteristics	Logistic regression	Exploratory

If the test for between–treatment-arm homogeneity of any baseline characteristic gives two-sided p-value <0.10, then the effect that baseline characteristic has on SCT rate will be quantified using LR. Two LR models will be fit. One model will include the baseline characteristic in question as the only independent variable, and the second model will include the baseline characteristic and the stratification factors used for randomization.

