4.5.3.4 Crossover (Stage 2)

- Patients randomized to CM with progressive disease or no response after one cycle of CM may cross over to receive ACM.
- Patients randomized to CM with a best response of PR after 2 cycles of CM may also cross over to receive ACM.

- Continued use of mitoxantrone is optional after completion of one cycle of ACM
- Mitoxantrone must be omitted from subsequent cycles if the patient's lifetime daunorubicin equivalent exceeds 460 mg/m² (see *Appendix G* for conversion table) or the left ventricular ejection fraction (LVEF) drops below 45%. Patients crossing over who meet the above criteria will receive only AC (alvocidib and cytarabine) for all cycles instead of ACM.
- Patients who cross over to ACM may receive up to a combined total (CM + ACM) of 4 cycles.

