11.4.2 Efficacy Analyses

Response assessments in Stage 1 are defined by the International Working Group and 2010 ELN Criteria [20, 21]. The 2017 ELN criteria will be used to determine patient responses during Stage 2 [23] (*Appendix E*). The primary analysis for these response rates will be performed using data from all enrolled patients (intent-to-treat, ITT). In the ITT analysis, patients withdrawing from the study for any reason prior to a response assessment will be classified as a nonresponder. A secondary analysis of per protocol patients will also be performed.

Primary Efficacy Endpoint

- Complete Remission (CR) rate = Percentage of patients achieving CR

Secondary Efficacy Endpoints

- Combined CR Rate = Percentage of patients achieving a CR, CRi or CRp[†]
- Combined Response Rate = Percentage of patients achieving a CR, CRi, CRp[†], or PR
- Overall Survival (OS) = Time from randomization (Day 1) until death from any cause
- Event-free Survival (EFS) = Time from randomization (Day 1) until (a) treatment failure, (b) relapse after CR, or (c) death from any cause, whichever occurs first, censored at 2 years
- Rate of Stem Cell Transplantation = Percentage of patients proceeding directly to stem cell transplantation

[†]Note that CRp has been retained in definitions for Combined CR Rate and Combined Remission Rate because Stage-1 patients were assessed using the IWG criteria. CRp will not be used for assessing response in Stage-2 patients and, therefore, will not be included in the definitions of Combined CR Rate and Combined Remission Rate in Stage 2.

The CR rate in patients failing CM and crossing over to receive ACM will also be determined.

Secondary endpoints described for Stage 1/Stage 2 will also be assessed.

Additional exploratory analyses may be performed to assist the sponsor in planning future studies.

Without taking appropriate measures, testing multiple efficacy parameters inflates the overall significance level since the probability of making a type-1 error in at least one from a set of hypothesis tests is greater than the probability of making a type-1 error in any single test. The hierarchical closed test procedure will be used to maintain the overall 2.5% significance level.

The order of efficacy endpoints for the hierarchical closed test procedure is:

1. CR rate
2. Combined CR rate
3. Combined Response Rate
4. OS

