PBSC	Peripheral Blood Stem Cells
PFS	Progression-Free Survival
PH	Proportional Hazards (model)

* The term CRp appears in this document to maintain compatibility with the study's case report forms, however CRp will not be used by the hematologists performing the central review of patients' responses and it is not expected to be used by the investigators.

PR	Partial Remission
PT	(MedDRA) Preferred Term
RFS	Relapse-Free Survival
ROC	Receiver Operating Characteristic (curve)
SAE	Serious Adverse Event
SAP	Statistical Analysis Plan
SCT	Stem Cell Transplant/Transplantation
SMQ	Standardized MedDRA Query
SOC	(MedDRA) System Organ Class
TEAE	Treatment Emergent Adverse Event
TLS	Tumor Lysis Syndrome
WHO	World Health Organization

3. Definitions

Standard statistical terminology (e.g., type-1 error rate and significance level) is omitted intentionally. Efficacy endpoints are defined in Section 4.1 below (see Table 1).

Baseline Value: last measured value prior to the first dose of study drug (or prior to randomization for patients not treated)

Combined CR: response assessment of CR, CRi or CRp

Combined Remission: response assessment of CR, CRi, CRp or PR

Crossover Patient: a patient randomized to CM who, following 1-2 cycles of CM, receives ACM as stipulated in the study protocol

Cycle 1: period of time from the first dose of study drug until the start of study drug in cycle 2 or the start of alternative AML therapy other than supportive measures such as blood product transfusions (hence a patient whose first response assessment in cycle 1 is a CRi or CRp is considered to have achieved CR if neutrophils and platelets recover prior to initiation of cycle 2 or alternative AML therapy)

Cycle-1 Combined CR Rate: percentage of patients who achieve a combined CR (CR, CRi or CRp) after one cycle of treatment

Cycle-1 Combined Remission Rate: percentage of patients who achieve a combined remission (CR, CRi, CRp or PR) after one cycle of treatment

Cycle-1 CR Rate: percentage of patients who achieve a CR after one cycle of treatment (see section 7.9.1)

Intent-to-Treat Population: all patients randomized to receive study drug regardless of whether they actually received study drug and regardless of whether evidence is found indicating they failed to meet study inclusion/exclusion criteria or had other protocol violations (see section 7.1)

Neutrophil Recovery: Absolute neutrophil count $\geq 1 \times 10^9/L$ following the administration of study drug

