Per-Protocol Population: The subset of safety patients who either (a) have at least one response assessment on study, or (b) die prior to their first scheduled response assessment; however, patients are excluded from the per-protocol population if they have an important protocol deviation, such as when evidence is found indicating they failed to meet any study inclusion/exclusion criterion (see section 7.1)

Platelet Recovery: Platelet count $\geq 100 \times 10^9/L$ following the administration of study drug

Pointwise: without controlling for multiple comparisons

Prestudy: Occurrence prior to randomization

Response-Available Population: The subset of safety patients who have at least one response assessment on study (see section 7.1)

Safety Population: The subset of intent-to-treat patients who received at least one dose of study drug (see section 7.1)

Sensitivity Analysis: study of how statistical methodology and assumptions affect results of the primary analysis

Shift Table: two-way frequency table pairing baseline value with the most extreme post-baseline result

Study Drug: alvocidib, Ara-C (cytarabine) and mitoxantrone

Supportive Analysis: synonymous with Sensitivity Analysis

Treatment Failure: failing to achieve a CR, CRi, CRp or PR following induction therapy (see section 7.9.2)

4. Introduction

This Statistical Analysis Plan (SAP) details the planned methodology for summarizing data collected in the clinical study conducted under Tolero, Inc. protocol TPI-ALV-201 and for comparing outcomes between the two treatment arms, ACM (alvocidib, Ara-C [cytarabine] and mitoxantrone) and CM (Ara-C [cytarabine] and mitoxantrone). The current version of the study protocol is Amendment 7 dated 30-MAY-2018. Future protocol amendments (if any) will be reviewed to assess whether the changes necessitate modification of this SAP.

Since the study protocol is a companion document to this SAP, aspects in the protocol unrelated to statistical issues (e.g., patient eligibility criteria, descriptions of clinical materials, and criteria for defining treatment failure, response to treatment and disease relapse) are not repeated here.

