
Secondary Efficacy Endpoints (not listed in order of importance)
 
• Cycle-1 Combined CR Rate: percentage of patients achieving a combined CR (CR, CRi or CRp) after one cycle of treatment• Cycle-1 Combined Remission Rate: percentage of patients achieving a combined remission (CR, CRi, CRp or PR) after one cycle of treatment• Overall Survival: time from the date of randomization (Day 1) until death from any cause• Progression-Free Survival: time from the date of randomization (Day 1) until (a) treatment failure, (b) relapse after combined remission (CR, CRi, CRp or PR), or (c) death from any cause, whichever occurs first• Relapse-Free Survival Following CR (defined only for patients who achieve a CR during the study): time from the date of CR (Day 1) until (a) relapse after CR, or (b) death from any cause, whichever occurs first• Relapse-Free Survival Following Combined CR (defined only for patients who achieve a combined CR during the study): time from the earliest date of combined CR (Day 1) until (a) relapse after combined CR, or (b) death from any cause, whichever occurs first• Relapse-Free Survival Following Combined Remission (defined only for patients who achieve a combined remission during the study): time from the earliest date of combined remission (Day 1) until (a) relapse after combined remission, or (b) death from any cause, whichever occurs first• CR Duration (defined only for patients who achieve a CR during the study): time from the date of CR (Day 1) until relapse after CR• Combined CR Duration (defined only for patients who achieve a combined CR during the study): time from the earliest date of combined CR (Day 1) until relapse after combined CR• Combined Remission Duration (defined only for patients who achieve a combined remission during the study): time from the earliest date of combined remission (Day 1) until relapse after combined remission• Stem Cell Transplant Rate: percentage of patients proceeding directly to stem cell transplantation within 90 days after their last dose of study drug

Table 1. Study Endpoints

Safety Endpoints (not listed in order of importance) 
• 30- and 60-Day Mortality• Adverse Event Incidence Rates• Time to neutrophil recovery $\geq 1 \times 10^9/L$• Time to platelet recovery $\geq 100 \times 10^9/L$• Presence and Severity of Tumor Lysis Syndrome• Clinical Laboratory Parameters• Vital Signs

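### SAP 7.9.3 lets a transplant reached through crossover ACM count as a CM success, so it does not implement the 'proceeding directly' endpoint

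*SAP*

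**What the plan says.** Three definitions of the transplant endpoint are in force.

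- Protocol 11.4.2: "Percentage of patients proceeding directly to stem cell transplantation", with no time window.
- SAP 4.1, Table 1: "percentage of patients proceeding directly to stem cell transplantation within 90 days after their last dose of study drug".
- SAP 7.9.3, which governs the calculation: "percentage of patients proceeding to SCT within 90 days after their last dose of study drug regardless of whether the patient remains enrolled". The word *directly* is absent.

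Neither document defines *directly*. The SAP definitions (section 3) give "Study Drug: alvocidib, Ara-C (cytarabine) and mitoxantrone", so ACM given after crossover is study drug. Protocol 4.5.3.4 permits it: "Patients randomized to CM with progressive disease or no response after one cycle of CM may cross over to receive ACM". CM patients whose best response is PR after two cycles may also cross over, and "Patients who cross over to ACM may receive up to a combined total (CM + ACM) of 4 cycles". The SAP defines a crossover patient as "a patient randomized to CM who, following 1-2 cycles of CM, receives ACM as stipulated in the study protocol".

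The primary transplant analysis (SAP Table 7) is a stratified CMH test on the ITT population, grouped by randomised arm (SAP 7.1). The endpoint is third of nine in the SAP hierarchy (7.5.2) and last of six in the protocol hierarchy (11.4.2).

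**The concern.** The endpoint is meant to show whether the assigned induction gets more patients to transplant. Under 7.9.3, a CM patient who fails, crosses over, remits on ACM and is transplanted within 90 days of the last ACM dose is a CM success. Alvocidib then contributes to the control rate. Only CM patients can cross over, so this route runs one way.

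The SAP guards against this elsewhere. Section 7.9.1 declines to use best response as the primary endpoint because crossover would confound it, and it ends cycle 1 at cycle 2 or at alternative AML therapy. The transplant rate has no comparable rule.

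The stake is power. In the SAP hierarchy a miss at third place stops testing of combined CR, combined remission, overall survival and the three duration endpoints. In the protocol hierarchy nothing lies below it.

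**Working it through.** **Design figures.** The documents state no transplant rate or power, so only the CR design can be reproduced.
- SAP, 70% v 40%: two-stage O'Brien-Fleming, information fraction 56/106, unpooled variance 0.7×0.3 + 0.4×0.6 = 0.45. The required drift is 3.2554, so N = 2 × 3.2554² × 0.45 / 0.30² = 105.97 (SAP: 106). The one-sided levels are 0.00321 and 0.02378, as in SAP Table 3.
- Protocol, 28 per arm, 70% v 30%: 0.40/√(0.42/28) − 1.960 = 1.306, giving power of 90.4% (stated 90%); a pooled variance gives 87.0%.

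**Window.**
- One CM cycle: last dose Day 4, window closes Day 94.
- One ACM cycle: last dose Day 9, window closes Day 99.
- CM, then crossover from Day 46: last dose Day 54, window closes Day 144.
- CM, then crossover at the 90-day limit between cycle starts (Day 91): last dose Day 99, window closes Day 189.

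**Which analysis would remove it?** None. ITT keeps crossover patients in CM. The SAP per-protocol set ignores crossover ACM when assigning treatment, so they stay in CM there too. The protocol's per-protocol rule (11.3) groups a patient as ACM if alvocidib precedes CR, which would move the same transplant to ACM.

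**Illustration of size.** Inputs, all assumptions unless sourced:
- Remission: ACM 70%; CM 40% (SAP) or 30% (protocol).
- Share of remissions transplanted: t = 73%, from 16/22 in Study 5 (Protocol Table 3).
- Share of CM failures crossing over: c = 50–70%, assumed.
- Remission after crossover, r: 4–6% from multi-refractory patients in Protocol Table 3 (0/10 in Study 2 and 1/16 in Study 5; pooled 1/26 = 4%, Study 5 alone 6%). 15% corresponds to 2/13 primary refractory in Study 2. 30–40% is the optimistic end (5/16 = 31% primary refractory in Study 5).

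CM rate = pCM × t + (1 − pCM) × c × r × t. ACM rate = 0.70 × 0.73 = 51.1%. Example: 0.40 × 0.73 + 0.60 × 0.70 × 0.15 × 0.73 = 29.2% + 4.6% = 33.8%.

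Power is by exact enumeration of the pooled two-proportion z test, one-sided 0.02378 (53 per arm) or 0.025 (28 per arm), unstratified and ignoring the hierarchy.

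| Crossover assumption | CM rate, 53/arm | Power | CM rate, 28/arm | Power |
|---|---|---|---|---|
| Direct transplants only | 29.2% | 63% | 21.9% | 64% |
| c 50–70%, r 4–6% | 30–31% | 55–60% | 23–24% | 56–60% |
| c 70%, r 15% | 33.8% | about 43% | 27.3% | 45% |
| c 50%, r 30% | 35.8% | 34% | 29.6% | 37% |
| c 70%, r 40% | 41.5% | 15% | 36.2% | 19% |

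The factor (1 − pCM) treats every patient without CR as eligible to cross over. CRi patients are not, so the added transplants are on the high side.

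**The case against.** **Counting by randomised arm is a legitimate treatment-policy estimand.** That stands, and its bias is conservative for a superiority claim. It is still not the *directly* endpoint that both documents name.

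**Table 1 joins *directly* to the 90-day window, so 90 days may be what the word means.** This is a fair reading and makes the wording partly an ambiguity. It does not deal with crossover, because crossover doses reset the clock.

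**The large losses rest on favourable inputs.** This stands. A crossover patient has relapsed or failed induction and has then failed CM, so the multi-refractory results are the closest data, although those studies were not selected on MCL-1. Study 5's 16/22 includes ALL and biphenotypic patients and has no 90-day limit. Study 2 gives 5/18 plus 1/2, that is 6/20 = 30%; with t = 30%, power is only about 24% at either sample size before any crossover.

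**A reader might infer that off-study salvage also favours CM.** The documents do not support that. Its inclusion is inferred from the absence of an exclusion, it is open to both arms, and it must fit within 49 days (CM) or 54 days (ACM) after a Day 45 assessment. Later on-study cycles restart the window in both arms too. Only crossover is one-sided.

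**The consequence depends on which document governs.** The SAP is tied to Amendment 7, while the protocol describes Amendment 11. Under the protocol, transplant is tested only if all five earlier endpoints succeed.

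**Conclusion.** The definition needs correcting. As written, 7.9.3 credits CM with transplants reached through crossover ACM, and no planned analysis isolates the direct ones. The result is dilution and loss of power, without inflation of type I error.

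The size is uncertain because the documents give neither crossover nor transplant rates. With remission after crossover near the protocol's multi-refractory results, the loss is modest: about 3 to 8 percentage points of power. It becomes severe only at 30–40% remission. A reader might take the 15% or 19% figure as the expected outcome; the protocol's own data do not support that, and those values belong at the far end of a range. The loss matters more under the SAP hierarchy than under the protocol's, where it is confined to this endpoint.

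**What to change.** In SAP 7.9.3, count a transplant as direct only if it occurs within 90 days after the last dose of the randomised regimen and before any of:
- a crossover dose;
- re-induction given for non-response, in either arm;
- any other non-transplant AML therapy.

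Conditioning and the transplant itself are not such therapy. This must be stated, because 7.9.1 lists transplant as alternative AML therapy and its cut-off cannot be borrowed literally. Patients who receive any of the three first count as not proceeding directly, in both arms. State also how continued treatment after a best response of PR at two cycles is counted, since CM patients may then cross over and ACM patients cannot.

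The symmetry is essential. Protocol 4.5.3.3 lets non-responders continue induction with Medical Monitor permission. If only CM crossovers were failed, ACM patients transplanted after a second ACM induction would still count. Take arms with equal remission, 50% of ACM non-responders re-induced, 6–30% of those remitting and t = 73%. The counted rates become 29.2% for CM and 30.5–35.8% for ACM at 53 per arm (remission 40%), and the one-sided error is about 3–11%. At 28 per arm (remission 30%) it is about 3–9%.

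Report all transplants by randomised arm, split by route, as the supportive treatment-policy analysis. Align protocol 11.4.2, SAP Table 1 and 7.9.3.

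Cost: SAP and protocol wording, and fewer counted transplants. The start date of other AML therapy must be available for every patient. Section 7.9.1 already needs it to end cycle 1, but the follow-up calls in protocol 5.6 do not list it and protocol 4.7.2 limits post-dose medication recording to treatment of adverse events, so the case report form should be checked.

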7.9.4. Overall Survival

OS time is defined for all patients and is measured from the date of randomization (Day 1) until death from any cause.

Rules for censoring OS time are:

- A patient with OS continuing as of the date he is lost to follow-up will have his OS time censored on the date of his last assessment of any type
- A patient with OS continuing as of the database lock will have his OS time censored on the date of his last assessment of any type

Hypothesis testing for OS will be based on the stratified log rank test statistic (see Table 6). Stratification levels will be the same as those used for the randomization scheme (see section 6). Two Cox PH models will be fit to provide estimates of the HR. One model will include treatment arm as the only independent variable, and the second model will include treatment arm and the stratification factors used for randomization. KM survival curves will be graphed for visual inspection of differences in OS between the treatment arms. Within-treatment-arm statistics will include the number and percentage of censored OS times, quartile OS times, 95% CIs for the quartile OS times, and KM survival percentages with 95% CIs at select milestone times (e.g., 6, 12 and 18 months). Between-treatment-arm statistics will include HRs from the Cox PH models and their 95% CIs.

Sensitivity analyses will be run with OS time censored on the date of BM or PBSC transplant.

If the test for between-treatment-arm homogeneity of any baseline characteristic gives two-sided p-value <0.10, then the effect that baseline characteristic has on OS time will be quantified using Cox PH modeling. Two PH models will be fit. One model will include the baseline characteristic in question as the only independent variable, and the second model will include the baseline characteristic and the stratification factors used for randomization.

7.9.5. Relapse-Free Survival Following CR

RFS time is defined only for patients who achieve a CR during the study and is measured from the date of CR (Day 1) until (a) relapse after CR, or (b) death from any cause, whichever occurs first.

An additional rule for defining RFS time is:

- A patient found to have relapsed after missing one or more scheduled response assessments will have his RFS time end on the scheduled date for the first missed response assessment following the last confirmation of CR

Rules for censoring RFS time are:

- A patient with RFS continuing as of the date he is lost to follow-up will have his RFS time censored on the date of his last response assessment
- A patient with RFS continuing as of the database lock will have his RFS time censored on the date of his last response assessment

Hypothesis testing for RFS will be based on the stratified log rank test statistic (see Table 6). Stratification levels will be the same as those used for the randomization scheme (see section 6). Two Cox PH models will be fit to provide estimates of the HR. One model will include treatment arm as the only independent variable, and the second model will include treatment arm and the stratification factors used for randomization. KM “survival” curves will be graphed for visual inspection of differences in RFS between the treatment arms. Within-treatment-arm statistics will include the number and percentage of patients who achieve a CR, the number and percentage of censored RFS times, quartile RFS times, 95% CIs for the quartile RFS times, and KM “survival” percentages with 95% CIs at select milestone times (e.g., 6, 12 and 18 months).

Between–treatment-arm statistics will include HRs from the Cox PH models and their 95% CIs.

Sensitivity analyses will be run with RFS time censored on the date of BM or PBSC transplant.

If the test for between–treatment-arm homogeneity of any baseline characteristic gives two-sided p-value <0.10, then the effect that baseline characteristic has on RFS time will be quantified using Cox PH modeling. Two PH models will be fit. One model will include the baseline characteristic in question as the only independent variable, and the second model will include the baseline characteristic and the stratification factors used for randomization.

Two endpoints analogous to relapse-free survival following CR will be analyzed using similar methods.

- Relapse-Free Survival Following Combined CR (defined only for patients who achieve a combined CR during the study): time from the earliest date of combined CR (Day 1) until (a) relapse after combined CR, or (b) death from any cause, whichever occurs first
- Relapse-Free Survival Following Combined Remission (defined only for patients who achieve combined remission during the study): time from the earliest date of combined remission (Day 1) until (a) relapse after combined remission, or (b) death from any cause, whichever occurs first

Response categories included in “combined CR” and “combined remission” are delineated in Section 3.

